9.2.1.3 Safety Assessment Methods

At each visit, the blinded Investigator or a delegate will perform a clinical or medically-driven physical examination and will ask the subject or subject's parent/LAR about any solicited reactions and unsolicited AEs recorded in the DC and/or MA, as well as about any other AEs that may have occurred since the previous visit. All relevant data will be transcribed into the CRB according to the instructions provided by the Sponsor.

9.2.1.3.1 Immediate Post-vaccination Observation Period

Subjects will be kept under observation for 30 minutes after each vaccination to ensure their safety. The post-vaccination observation should be documented in the source document. Any AE that occurs during this period will be noted on the source document and recorded in the CRB, as follows:

- Unsolicited systemic AEs will be recorded as immediate AEs in the CRB (presence marked as "yes" and details collected)
- Solicited and unsolicited injection site reactions and solicited systemic reactions will be recorded in the CRB in the same way as any reactions starting on the day of vaccination
- SAEs will be recorded in the CRB and reported to the Sponsor in the same way as any other SAEs, according to the procedures described in [Section 10](#)

9.2.1.3.2 Reactogenicity (Solicited Reactions From Day 0 to Day 7 After Each Vaccination)

After each vaccination, subjects or subjects' parent/LAR will be provided with a DC, a digital thermometer, and a flexible ruler, and will be instructed how to use them. The following items will be recorded by the subjects in the DC on the day of vaccination and for the next 7 days (ie, D0 through D7) until resolution:

- Daily temperature, with the route by which it was taken

- Daily measurement or intensity grade of all other solicited injection site and systemic reactions
- Action taken for each event (eg, medication)

The action(s) taken by the subject or subject's parent/LAR to treat and/or manage any **solicited reactions** will be classified in the CRB using the following list (all applicable items should be checked):

- None
- Medication
- Health care provider contact
- Hospitalized
- Discontinuation of study vaccination

[Table 9.1](#) to [Table 9.3](#) and [Table 9.4](#) to [Table 9.5](#) present, respectively, the injection site reactions and systemic reactions that are pre-listed in the DCs and CRB, together with the intensity scales.

Table 9.1: Solicited injection site reactions: terminology, definitions, and intensity scales in infants and toddlers aged ≤ 23 months

CRB term (MedDRA lowest level term [LLT])*	Injection site tenderness	Injection site erythema	Injection site swelling
MedDRA PT†	Injection site pain	Injection site erythema	Injection site swelling
Diary card term	Tenderness	Redness	Swelling
Definition	Pain when the injection site is touched or injected limb mobilized	Presence of a redness including the approximate point of needle entry	Swelling at or near the injection site Swelling or edema is caused by a fluid infiltration in tissue or cavity and, depending on the space available for the fluid to disperse, swelling may be either soft (typically) or firm (less typical) to touch and thus can be best described by looking at the size of the swelling
Intensity scale§	Grade 1: Minor reaction when injection site is touched Grade 2: Cries or protests when injection site is touched Grade 3: Cries when injected limb is mobilized, or the movement of the injected limb is reduced	Grade 1: > 0 to < 25 mm Grade 2: ≥ 25 to < 50 mm Grade 3: ≥ 50 mm	Grade 1: > 0 to < 25 mm Grade 2: ≥ 25 to < 50 mm Grade 3: ≥ 50 mm

* The MedDRA (Version 22.0 or higher) lowest level term (LLT) will be used in the protocol and CRF

† The MedDRA LLT will be used in the protocol and in analyzing and reporting the reactions (clinical study report, summary documents)

§ For the subjective reaction of tenderness, parents / legally acceptable representatives will record the intensity level (Grade 1, 2, or 3) in the diary card. For the measurable reactions of redness and swelling, they will record just the size of the reaction, and the classification as Grade 1, 2, or 3 will be assigned at the time of the statistical analysis.

Table 9.2: Solicited injection site reactions: terminology, definitions, and intensity scales in children (aged 2 through 11 years)

CRB term (MedDRA lowest level term [LLT])*	Injection site pain	Injection site erythema	Injection site swelling
MedDRA PT†	Injection site pain	Injection site erythema	Injection site swelling
Diary card term	Pain	Redness	Swelling
Definition	Pain either present spontaneously or when the injection site is touched or injected limb is mobilized	Presence of a redness including the approximate point of needle entry	Swelling at or near the injection site Swelling or edema is caused by a fluid infiltration in tissue or cavity and, depending on the space available for the fluid to disperse, swelling may be either soft (typically) or firm (less typical) to touch and thus can be best described by looking at the size of the swelling
Intensity scale§	Grade 1: Easily tolerated Grade 2: Sufficiently discomforting to interfere with normal behavior or activities Grade 3: Incapacitating, unable to perform usual activities	Grade 1: > 0 to < 25 mm Grade 2: ≥ 25 to < 50 mm Grade 3: ≥ 50 mm	Grade 1: > 0 to < 25 mm Grade 2: ≥ 25 to < 50 mm Grade 3: ≥ 50 mm

* The MedDRA (Version 22.0 or higher) lowest level term (LLT) will be used in the protocol and CRF

† The MedDRA LLT will be used in the protocol and in analyzing and reporting the reactions (clinical study report, summary documents)

§For the subjective reaction of pain, subjects or parents / legally acceptable representatives will record the intensity level (Grade 1, 2, or 3) in the diary card. For the measurable reactions of redness and swelling, they will record just the size of the reaction, and the classification as Grade 1, 2, or 3 will be assigned at the time of the statistical analysis.

Table 9.3: Solicited injection site reactions: terminology, definitions, and intensity scales in adolescents and adults (aged ≥ 12 years)

CRB term (MedDRA lowest level term [LLT])*	Injection site pain	Injection site erythema	Injection site swelling
MedDRA PT†	Injection site pain	Injection site erythema	Injection site swelling
Diary card term	Pain	Redness	Swelling
Definition	Pain either present spontaneously or when the injection site is touched or injected limb is mobilized	Presence of a redness including the approximate point of needle entry	Swelling at or near the injection site Swelling or edema is caused by a fluid infiltration in tissue or cavity and, depending on the space available for the fluid to disperse, swelling may be either soft (typically) or firm (less typical) to touch and thus can be best described by looking at the size of the swelling
Intensity scale§	Grade 1: A type of AEs that is usually transient and may require only minimal treatment or therapeutic intervention. The event does not generally interfere with usual activities of daily living. Grade 2: A type of AEs that is usually alleviated with additional therapeutic intervention. The event interferes with usual activities of daily living, causing discomfort but poses no significant or permanent risk of harm to the research subject. Grade 3: A type of AEs that interrupts usual activities of daily living, or significantly affects clinical status, or may require intensive therapeutic intervention.	Grade 1: ≥ 25 to ≤ 50 mm Grade 2: ≥ 51 to ≤ 100 mm Grade 3: > 100 mm	Grade 1: ≥ 25 to ≤ 50 mm Grade 2: ≥ 51 to ≤ 100 mm Grade 3: > 100 mm

* The MedDRA (Version 22.0 or higher) lowest level term (LLT) will be used in the protocol and CRF

† The MedDRA LLT will be used in the protocol and in analyzing and reporting the reactions (clinical study report, summary documents)

§ For the subjective reaction of pain, subjects or parents / legally acceptable representatives will record the intensity level (Grade 1, 2, or 3) in the diary card. For the measurable reactions of redness and swelling, they will record just the size of the reaction, and the classification as Grade 1, 2, or 3 will be assigned at the time of the statistical analysis

Table 9.4: Solicited systemic reactions: terminology, definitions, and intensity scales in infants and toddlers aged ≤ 23 months

CRB term (MedDRA lowest level term [LLT])*	Fever	Vomiting	Crying abnormal	Drowsiness	Appetite lost	Irritability
MedDRA PT†	Pyrexia	Vomiting	Crying	Somnolence	Decreased appetite	Irritability
Diary card term	Temperature	Vomiting	Abnormal crying	Drowsiness	Loss of appetite	Irritability
Definition	Elevation of temperature to $\geq 38.0^{\circ}\text{C}$ ($\geq 100.4^{\circ}\text{F}$)	Vomiting does not include spitting up	Inconsolable crying without a determined reason	Reduced interest in surroundings, or increased sleeping	See intensity scale	An excessive response to stimuli: increased fussiness, whining, and fretfulness despite attempts to comfort the toddler and despite caregiver responses that would normally be soothing
Intensity scale§	Grade 1: $\geq 38.0^{\circ}\text{C}$ to $\leq 38.5^{\circ}\text{C}$ or $\geq 100.4^{\circ}\text{F}$ to $\leq 101.3^{\circ}\text{F}$ Grade 2: $> 38.5^{\circ}\text{C}$ to $\leq 39.5^{\circ}\text{C}$ or $> 101.3^{\circ}\text{F}$ to $\leq 103.1^{\circ}\text{F}$ Grade 3: $> 39.5^{\circ}\text{C}$ or $> 103.1^{\circ}\text{F}$	Grade 1: 1 episode per 24 hours Grade 2: 2–5 episodes per 24 hours Grade 3: ≥ 6 episodes per 24 hours or requiring parenteral hydration	Grade 1: < 1 hour Grade 2: 1–3 hours Grade 3: > 3 hours	Grade 1: Sleepier than usual or less interested in surroundings Grade 2: Not interested in surroundings or did not wake up for a feed / meal Grade 3: Sleeping most of the time or difficult to wake up	Grade 1: Eating less than normal Grade 2: Missed 1 or 2 feeds / meals completely Grade 3: Refuses ≥ 3 feeds / meals or refuses most feeds / meals	Grade 1: Easily consolable Grade 2: Requiring increased attention Grade 3: Inconsolable

* The MedDRA (Version 22.0 or higher) lowest level term (LLT) will be used in the protocol and CRF

† The MedDRA LLT will be used in the protocol and in analyzing and reporting the reactions (clinical study report, summary documents)

§ For all reactions but fever, parents / legally acceptable representatives will record the intensity level (Grade 1, 2, or 3) in the diary card. For fever, they will record the body temperature, and the classification as Grade 1, 2, or 3 will be assigned at the time of the statistical analysis based on the unit used to measure the temperature and the intensity scale.

Table 9.5: Solicited systemic reactions: terminology, definitions, and intensity scales in children (aged 2 through 11 years), adolescents or adults (aged ≥ 12 years)

CRB term (MedDRA lowest level term [LLT])*	Fever	Headache	Malaise	Myalgia
MedDRA PT†	Pyrexia	Headache	Malaise	Myalgia
Diary card term	Temperature	Headache	Feeling unwell	Muscle aches and pains
Definition	Elevation of temperature to $\geq 38.0^{\circ}\text{C}$ ($\geq 100.4^{\circ}\text{F}$)	Pain or discomfort in the head or scalp. Does not include migraine.	General ill feeling Malaise is a generalized feeling of discomfort, illness, or lack of well-being that can be associated with a disease state. It can be accompanied by a sensation of exhaustion or inadequate energy to accomplish usual activities.	Muscle aches and pains are common and can involve more than one muscle at the same time. Muscle pain can also involve the soft tissues that surround muscles. These structures, which are often referred to as connective tissues, include ligaments, tendons, and fascia (thick bands of tendons). Does not apply to muscle pain at the injection site which should be reported as injection site pain.
Intensity scale§	Grade 1: $\geq 38.0^{\circ}\text{C}$ to $\leq 38.4^{\circ}\text{C}$, or $\geq 100.4^{\circ}\text{F}$ to $\leq 101.1^{\circ}\text{F}$	Grade 1: A type of AEs that is usually transient and may require only minimal treatment or therapeutic intervention. The event does not generally interfere with usual activities of daily living.	Grade 1: A type of AEs that is usually transient and may require only minimal treatment or therapeutic intervention. The event does not generally interfere with usual activities of daily living.	Grade 1: A type of AEs that is usually transient and may require only minimal treatment or therapeutic intervention. The event does not generally interfere with usual activities of daily living.

CRB term (MedDRA lowest level term [LLT])*	Fever	Headache	Malaise	Myalgia
MedDRA PT†	Pyrexia	Headache	Malaise	Myalgia
Diary card term	Temperature	Headache	Feeling unwell	Muscle aches and pains
	Grade 2: $\geq 38.5^{\circ}\text{C}$ to $\leq 38.9^{\circ}\text{C}$, or $\geq 101.2^{\circ}\text{F}$ to $\leq 102.0^{\circ}\text{F}$	Grade 2: A type of AEs that is usually alleviated with additional therapeutic intervention. The event interferes with usual activities of daily living, causing discomfort but poses no significant or permanent risk of harm to the research subject. Grade 3: A type of AEs that interrupts usual activities of daily living, or significantly affects clinical status, or may require intensive therapeutic intervention.	Grade 2: A type of AEs that is usually alleviated with additional therapeutic intervention. The event interferes with usual activities of daily living, causing discomfort but poses no significant or permanent risk of harm to the research subject. Grade 3: A type of AEs that interrupts usual activities of daily living, or significantly affects clinical status, or may require intensive therapeutic intervention.	Grade 2: A type of AEs that is usually alleviated with additional therapeutic intervention. The event interferes with usual activities of daily living, causing discomfort but poses no significant or permanent risk of harm to the research subject. Grade 3: A type of AEs that interrupts usual activities of daily living, or significantly affects clinical status, or may require intensive therapeutic intervention.

* The MedDRA (Version 22.0 or higher) lowest level term (LLT) will be used in the protocol and CRF

† The MedDRA LLT will be used in the protocol and in analyzing and reporting the reactions (clinical study report, summary documents)

§ For all reactions but fever, subjects or parents / legally acceptable representatives will record the intensity level (Grade 1, 2, or 3) in the diary card. For fever, they will record the body temperature, and the classification as Grade 1, 2, or 3 will be assigned at the time of the statistical analysis based on the unit used to measure the temperature and the intensity scale.

Important Notes for the Accurate Assessment of Temperature:

Subjects or subjects' parents/legally acceptable representatives are to measure body temperature once per day, preferably always at the same time. The optimal time for measurement is the evening, when body temperature is the highest. Temperature is also to be measured at the time of any apparent fever. The observed daily temperature and the route of measurement are to be recorded in the DC/MA, and the highest temperature will be recorded by the site in the CRB. The preferred route for this study is axillary for toddlers and children; oral for adolescent and adults. Pre-vaccination temperature is also systematically collected by the Investigator on the source document. Tympanic thermometers must not be used.

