An unsolicited AE is an observed AE that does not fulfill the conditions pre-listed in the CRB in terms of diagnosis and/or onset window post-vaccination. For example, if headache between D0 and D7 is a solicited reaction (ie, pre-listed in the protocol and CRB), then a headache starting on D7 is a solicited reaction, whereas headache starting on D8 post-vaccination is an unsolicited AE. Unsolicited AEs includes both serious (SAEs) and non-serious unsolicited AEs.

Injection Site Reaction:

An injection site reaction is an AR at and around the injection site. Injection site reactions are commonly inflammatory reactions. They are considered to be related to the product administered.

Systemic AE:

Systemic AEs are all AEs that are not injection or administration site reactions. They, therefore, include systemic manifestations such as headache, fever, as well as localized or topical manifestations that are not associated with the vaccination or administration site (eg, erythema that is localized but that is not occurring at the injection site).

Adverse Event of Special Interest (AESI):

An AESI is one of scientific and medical concern specific to the Sponsor's product or program, for which ongoing monitoring and rapid communication by the Investigator to the Sponsor can be appropriate. Such an event might warrant further investigation in order to characterize and understand it. Depending on the nature of the event, rapid communication by the study Sponsor to other parties (eg, regulators) might also be warranted.

AEs of special interest are AEs that are considered by the Sponsor to be relevant for the monitoring of the safety profile of the investigational vaccine. The following AESIs are defined: anaphylactic reactions, encephalitis, and convulsions.

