9.2.1.2 Safety Endpoints

The secondary endpoints for the evaluation of safety are:

- Occurrence of any unsolicited systemic AEs reported in the 30 minutes after each vaccine injection
- Occurrence of solicited (pre-listed in the subject's DC and electronic CRF) injection site and systemic reactions occurring within 7 days after each injection
- Occurrence of unsolicited (spontaneously reported) injection site reactions occurring within 28 days after each injection and unsolicited systemic AEs up to 28 days after each injection
- Occurrence of SAEs and AESIs within at least 6 months after each vaccination as applicable to Cohort 1 and Cohort 2.
- SAEs (including AESIs) reported throughout the study, including occurrence, nature (Medical Dictionary for Regulatory Activities [MedDRA] preferred term), time of onset, duration, intensity, action taken, relationship to the product administered (for systemic AEs only),

whether the event caused termination from the study, outcome, elapsed time from last administration (if less than 24h), relationship to study procedures, and seriousness criterion

Note: The following AESIs will be considered as SAEs and reported to the Sponsor: anaphylactic reactions, encephalitis, and convulsions. For each AESI, the standard case definitions from the Brighton Collaboration will be used. These AESIs have been defined based on existing post-marketing safety data of other rabies vaccines.

Note: Information about SAEs, AESIs, and cases of pregnancy were recorded throughout the study for pediatrics and adults in Cohort 1; and this is up to 6 months after the booster dose for subset of adults in Cohort 1. Information about SAEs, AESIs, and cases of pregnancy will be recorded until 6 months after the primary series (V05) and until 6 months after the booster dose for subset of adults in Cohort 2. Between the 6-month follow-up visit after primary series (V05) and booster dose visit (V08), AESIs will not be collected, only fatal SAEs and related SAEs will be collected.

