#### 4.3.1.1   Solicited Reactions

##### 4.3.1.1.1   Daily Intensity

All daily records for solicited reactions will be derived into daily intensity according to the following classification: None, Grade 1, Grade 2, Grade 3, or Missing (Unknown).

For the derivation of daily intensities, the following sequential steps will be applied:

- 1) Solicited reactions (except Fever/Pyrexia) with eCRF presence recorded as "No" and with all daily records missing (Unknown) then all daily intensities will be derived as None.
- 2) For a temperature partially missing after decimal point, the data will be analyzed replacing "MD" (missing data) by zero. For example, a "39.MD" daily temperature will be considered as "39.0°C" at the time of analysis.
- 3) For non-measurable solicited reactions, daily intensities will correspond to daily records reported in the clinical database. For measurable solicited reactions the daily measurements reported in the clinical database will be converted based upon the intensity scales defined in the protocol; this assumes a reaction that is too large to measure (non-measurable, "NM") is Grade 3. Note the intensity could be considered "None" (not a reaction) in the analysis despite being considered a reaction by the investigator (eg, swelling measurement  $> 0$  mm but  $< 25$  mm in subjects aged  $\geq 12$  years).

Note: The maximum intensity on the ongoing period is derived from the record of the maximum intensity/measurement after the end of the solicited period following the rule described above.

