##### 4.3.1.1.2   Maximum Overall Intensity

Maximum overall intensity is derived from the daily intensities computed as described in [Section 4.3.1.1.1](#) and is calculated as the maximum of the daily intensities over the period considered.

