##### 4.3.1.2.2 Intensity

Intensity for unsolicited AEs will be derived according to the following classification: Grade 0 (None), Grade 1, Grade 2, Grade 3, or Missing

If the unsolicited AE is measurable and its preferred term is part of the list of solicited reactions, then the measurement is derived based upon and following the same rule of the intensity scales defined in the protocol for that measurable injection site or systemic reaction. Note the intensity could be considered as “None” (not a reaction) in the analysis despite being considered a reaction by the investigator (eg, swelling measurement  $> 0$  mm but  $< 25$  mm in subject aged  $\geq 12$  years).

Intensity for the other unsolicited AEs will correspond to the value reported in the eCRF.

The maximum intensity corresponds to the highest intensity for a unique term.

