### ***Solicited Reactions***

The solicited injection site reactions and the solicited systemic reactions will be presented according to the term listed in the eCRF, separately.

The solicited injection site and systemic reactions will be analyzed within 7 days after each vaccination.

Each type of solicited reactions will be presented after each injection according to:

*- Maximum intensity during the solicited period:*

- Grade 1
- Grade 2
- Grade 3

*- Time of onset categories are in [Table 5.3](#)*

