**Table 5.5: Range of overall number of days of occurrence categories for solicited reactions**

	Injection Site Reactions	Systemic Reactions
Post each dose in the primary series, booster dose	1 - 3 days* 4 - 7 days 8 days or more Missing end date	1 - 3 days* 4 - 7 days 8 days or more Missing end date

\* For solicited reactions still ongoing at D08 after each dose, the range of overall number of days of occurrence category will be 2-3 days, 4-7 day, 8 days or more, and missing end date.

Note: Cohort 1 planned to receive 3 doses and Cohort 2 planned to receive 2 doses, respectively, in the primary series.

- *Action Taken:*

- Missing
- None
- Medication
- Health care provider contact
- Hospitalization
- Discontinuation of study vaccination

Solicited reaction after any injection in the primary series

“After any injection” is for primary series only, means after all scheduled vaccine injections of the primary vaccination series, and at least after the first vaccine injection (D0).

The solicited reaction will be presented after any injections in the primary series and presented after booster vaccination according to:

- *Occurrence during the solicited period for solicited reactions, and overall occurrence for solicited reactions still ongoing at D08*
- *Time of onset period*
- *Intensity grade: the maximum intensity grade will be computed during the solicited period for all solicited reactions*

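### Intensity of solicited reactions is tabulated over D0-D7 only, so a later peak that is already recorded and derived stays out of the specified intensity tables

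*Protocol*

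**What the plan says.** **Collection.** Protocol Section 9.2.1.3.2 has subjects record solicited reactions "on the day of vaccination and for the next 7 days (ie, D0 through D7) until resolution". Protocol Section 9.2.1.1 classifies by onset. If headache is pre-listed for D0 to D7, "then a headache starting on D7 is a solicited reaction, whereas headache starting on D8 post-vaccination is an unsolicited AE". A reaction that starts by D7 and worsens later therefore remains a solicited reaction.

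**Endpoint.** Protocol Section 9.2.1.2 defines the solicited endpoint as "injection site and systemic reactions occurring within 7 days after each injection".

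**Derivation.** SAP Section 4.3.1.1.2 takes the maximum overall intensity from the daily intensities; it "is calculated as the maximum of the daily intensities over the period considered". SAP Section 4.3.1.1.1 adds a separate variable: "The maximum intensity on the ongoing period is derived from the record of the maximum intensity/measurement after the end of the solicited period". SAP Section 4.3.1.1.7 uses that variable, together with the last daily grade, to decide whether a reaction is ongoing. No other use is stated.

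**Tables.** After each injection, SAP Section 5.1.2.2 presents "Maximum intensity during the solicited period". After any primary injection, and after the booster, "the maximum intensity grade will be computed during the solicited period for all solicited reactions". Beyond D7 the SAP presents whether a reaction was still ongoing at D8 and its total number of days (Table 5.5), but no grade.

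**Carry-over.** SAP Sections 4.3.1.1.4 and 5.1.2.2 have a rule for systemic reactions still present at the next vaccination. If the reaction then worsens, it is split, and the worsened part is counted under the later dose.

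**The concern.** Severity and duration are followed over different lengths of time. Duration runs to the end of the reaction, while the tabulated grade is cut off at D7, although the later maximum is in the database and is derived. A solicited reaction that is Grade 1 on D7 and Grade 3 on D9 is tabulated as Grade 1. Because its onset was inside the window, it does not move to the unsolicited tables.

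Describing safety after each injection is a secondary objective. Truncation can lower a reported grade but never raise it. Reactions that start late in the window are the most exposed: one that starts on D7 is graded on a single diary day.

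**Working it through.** There is no published figure to reproduce. The check applies the SAP rules to constructed diaries and then sizes one affected subject.

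**Inputs.** The solicited period is D0 to D7, which is 8 days. Swelling grades for subjects aged 12 years and over come from Protocol Table 9.3: below 25 mm is not graded, and above 100 mm is Grade 3. Total days for an ongoing reaction follow SAP Section 4.3.1.1.6: (end day) + (days present in the solicited period) - 8 + 1.

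**Constructed cases (assumed diaries).**

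| Case | Up to D7 | After D7 | Tabulated maximum | Maximum over solicited plus ongoing period |
|---|---|---|---|---|
| (a) Injection-site pain, ends D10 | Grade 1 on D5-D7 | Grade 3 | Grade 1 | Grade 3 |
| (b) Adult swelling | 20 mm on D5-D7 | 110 mm | None | Grade 3 |
| (c) Systemic, after dose 3, ends D10 | Grade 1 on D6-D7 | Grade 3 on D9 | Grade 1 | Grade 3 |
| (d) Systemic, after dose 1, dose 2 on D7 | Grade 1 before dose 2 | Grade 3 on D9 | Grade 1 under dose 1, Grade 3 under dose 2 | Already captured |

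- In (a) the total duration is 10 + 3 - 8 + 1 = 6 days, and in (c) it is 10 + 2 - 8 + 1 = 5 days. Both include the days after D7, while the grade does not.
- In (b) every daily intensity is None, so SAP Section 4.3.1.1.3 gives no presence. SAP Section 4.3.1.1.7 gives not ongoing, because the last daily grade is None, whatever was recorded later. This assumes that the site keeps the swelling as one solicited record; the documents do not say that it would be re-entered as an unsolicited event.
- In (d) dose 2 falls on D7 (+1 day), so the carry-over rule puts the Grade 3 under dose 2 and hence into the after-any-injection summary.

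**Where the gap remains.** The carry-over rule is written for systemic reactions only. The gap therefore covers:
- injection-site reactions after any dose;
- systemic reactions after the last primary dose;
- systemic reactions after dose 2 in Cohort 1, unless still ongoing at D28;
- systemic reactions after the booster.

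**Size of one affected subject.** 1/303 = 0.33%; 1/101 = 0.99%; 1/46 = 2.2%; 1/34 = 2.9%.

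**Illustration only.** Suppose that 1% to 5% of subjects have a reaction ongoing at D8, and that 5% to 20% of those reach Grade 3 only after D7. Then 1% x 5% = 0.05% to 5% x 20% = 1.0% of subjects are affected, or 0.15 to 3 of 303. Neither input comes from the documents.

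**The case against.** The strongest reply is that the SAP does what the protocol asks. The endpoint is a 7-day endpoint, and the tables say that the grade is the maximum in the solicited period, so nobody is misled about what is shown. Persistence past D7 is reported through the ongoing category and total duration. The objective is descriptive, with no hypothesis test, and the rule is the same for every vaccine group. All of this stands. What it leaves open is that the 7-day window fixes which reactions qualify, while severity data collected after it have no place in the specified intensity tables.

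A reader might go further in four ways that the documents do not support.

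- *A late Grade 3 appears in no table.* Case (d) shows otherwise for systemic reactions that worsen after the next dose. A late peak that met SAE criteria would be in the SAE tables, although without a stated grade breakdown. The table and listing shells are not among the documents, so the gap can be claimed only for the tables that the SAP specifies.
- *The SAP ignores data after D7.* It derives the later maximum; it does not tabulate it.
- *Unsolicited events are graded by a different, peak-based rule.* SAP Section 4.3.1.2.2 says that "The maximum intensity corresponds to the highest intensity for a unique term". This can equally be a rule for choosing among several records of one term. For events without a measured scale, the grade is simply the one entered in the eCRF, and the documents do not say that it is the peak over time.
- *The rule favours VRVg-2.* It applies to all groups alike, and nothing in the documents shows a difference between groups in late peaks.

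A further objection concerns the remedy. Adding the later maximum to every dose without conditions could assign one Grade 3 that follows dose 2 to both doses. That is right, and the fix allows for it.

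**Conclusion.** The point holds as a small reporting gap. The specified solicited-intensity tables stop at D7, although the later maximum is recorded and derived. For injection-site reactions after any dose, and for systemic reactions with no intervening dose, a later peak is not shown at its grade. Measured swelling or redness below 25 mm up to D7 in subjects aged 12 years and over can drop out of the solicited analysis altogether.

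The effect can only lower the whole-episode severity shown. One subject moves the Grade 3 rate by 0.33 to 2.9 points, depending on the group. How many subjects are affected cannot be estimated from the documents; the number is probably low. The conclusion rests on the wording of the SAP rules and not on any assumed rate. It is worth making because it is cheap, and it does not put the main safety conclusions in doubt.

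**What to change.** Keep the D0-D7 maximum as the main line in SAP Section 5.1.2.2, so that the tables still match the endpoint and stay comparable with the other VRVg studies. Then:

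1. Add a supplementary line, after each injection, after any primary injection and after the booster, giving the maximum intensity over the solicited plus ongoing period.
2. Use the ongoing-period maximum from SAP Section 4.3.1.1.1 wherever it is recorded, and do not make it conditional on the D7 grade. Otherwise case (b) is still missed.
3. For systemic reactions ongoing at the next vaccination, apply the existing attribution rule in SAP Sections 4.3.1.1.4 and 5.1.2.2, so that worsening after the later dose is not also assigned to the earlier one.

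The cost is a few lines of SAP text, one derivation and one extra table line, with no new data. On the supplementary line, Grade 3 rates can only equal the D0-D7 rates or be slightly higher.
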